1.2 Aim

The aim of the investigation is to demonstrate that the ATB System provides an improvement in hearing outcomes and quality of life compared to unaided hearing in patients with a conductive or mixed hearing loss or single-sided sensorineural deafness (SSD).

The aim is also to measure and present preoperative audiological test results with a Baha BP110 Power Sound Processor on a Baha Softband in relation to the Investigational device. Safety parameters will be collected.

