4 DESIGN OF THE CLINICAL INVESTIGATION

4.1 Design of the clinical investigation

This clinical investigation is an open, two armed, prospective, multicentre clinical investigation and is divided into a 3-month period (primary efficacy analysis) followed by an additional 9 months of follow-up for the complete 12 months period. The primary safety endpoint is 6 months. One arm is selected for conductive and mixed hearing loss subjects, the other arm is selected for single-sided sensorineural deafness subjects. Each subject will be compared to his/her own preoperative unaided hearing situation, with the Baha BP110 Power Sound Processor on a softband preoperatively and with the Investigational device at 3 months. If applicable subjects with a current hearing amplification will also be tested preoperatively.

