10.5.2 Secondary efficacy analyses

The second efficacy analyses will be performed for Investigational Device vs. Unaided. Baha BP110 Power Sound Processor on a Baha Softband will be presented (where applicable) but not compared to Investigational Device.

- APHAB
- Threshold audiometry: PTA4 (Mean of 500, 1000, 2000 and 4000 Hz)
- Threshold audiometry: 250, 500, 1000, 2000, 3000, 4000 and 6000 Hz
- Adaptive speech recognition in noise (50% performance)
- Speech in quiet (50dB, 65dB and 80dB)
- HUI-III (compared with current hearing situation)
- SSQ
- Choice of SP magnet
- BC Direct
- Feedback measurements. Investigational device

The secondary analyses will be presented for ITT and PP populations.

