4 STATISTICAL METHODOLOGY

4.1 General Methodology

Since all included subjects will have measurements of the primary and important secondary efficacy variables for unaided hearing, with the Investigational device and with a Baha power sound processor on a Baha Softband, all statistical analyses will be paired. All statistical analyses will be non-parametric. In order to choose the most powerful test, the Fisher's non-parametric permutation test for paired observations will be used for all paired analyses of continuous variables. The permutation tests use the measured values and not only the ranks in the calculations. For paired analysis of dichotomous and ordered categorical variables the Sign test will be used.

The analyses will be performed in the following priority:

1. Investigational Device vs. Unaided
2. Investigational Device vs. Baha power sound processor on a Baha Softband

In addition to the change variables the distribution of all efficacy variables will be presented by visit, where applicable.

The main efficacy analysis will be performed on the ITT population and complementary efficacy analyses will be performed on the PP population. The main analysis will be performed after the 3 month visit. A complementary analysis will be performed 9 months after the main analysis (12-month visit). All significance tests will be one-sided and performed at the 2.5% significance level to demonstrate an improvement with Investigational Device.

The hierarchical testing procedure below is introduced to guarantee that the probability of Type I error is < 2.5% for all confirmative statements. The order of the hierarchical testing procedure will be:

1. PTA 4 pre-operative unaided vs 3 months (Primary efficacy analysis)
2. Adaptive speech recognition in noise (50% performance), speech to noise ratio (SNR) pre-operative unaided vs 3 months
3. Speech in quiet at 65dB SPL pre-operative unaided vs 3 months
4. APHAB Global pre-operative unaided vs 3 months aided
5. Hearing attribute (HUI-III) pre-operative unaided vs 3 months
6. Mean of the 12 items in the SSQ pre-op unaided vs 3 months

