- Adaptive speech recognition in noise (50% performance) at 4 weeks, 3, 6 and 12 months
- Speech in quiet (50dB, 65dB and 80dB) at 4 weeks, 3, 6 and 12 months
- Feedback measurement at each frequency at 4 and 6 weeks, 3, 6 and 12 months
- HUI-III at 3, 6 and 12 months
- SSQ at 3, 6 and 12 months

Comparison of the Investigational device with a Baha Power sound processor worn on a Baha Softband will be done according to the general methodology with Fisher's non-parametric permutation test for paired observations for the following variables:

- Threshold audiometry: PTA4 (Mean of 500, 1000, 2000 and 4000 Hz) at 4 weeks, 3, 6 and 12 months
- Threshold audiometry: 250, 500, 1000, 2000, 3000, 4000 and 6000 Hz at 4 weeks, 3, 6, and 12 months

STATISTISKA KONSULTGRUPPEN		Statistical Analysis Plan	
Protocol: Clinical performance of a new implant system for bone conduction hearing		Protocol No: CBAS5539	
		Version: 1.0	Page 18 of 22

- Adaptive speech recognition in noise (50% performance) at 4 weeks, 3, 6 and 12 months
- Speech in quiet (50dB, 65dB and 80dB) at 4 weeks, 3, 6 and 12 months
- BC Direct at 4 and 6 weeks, 3, 6 and 12 months.

Choice of SP magnet and change of SP magnet. Changes in SP magnet strength will also be presented graphically in a flow graph.

All secondary efficacy analyses will be performed for both the ITT population and PP population. PTA4 will also be analysed for the PP population in the same fashion as in the primary analysis.

Analyses of Threshold Audiometry, Adaptive speech recognition in noise and Speech in quiet, BC Direct, HUI, APHAB and SSQ will be made totally and also by SSD and Conductive/Mixed patients. This will be made only for the ITT population.

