6 CHANGES OF ANALYSIS FROM PROTOCOL

No changes of the analyses according to the protocol are made.

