- Table 14.2.10.2 Adaptive speech recognition in noise and Speech in quiet ATB System vs Unaided (SSD patients ITT Population)
- Table 14.2.10.3 BC Direct (SSD patients ITT Population)
- Table 14.2.10.4 HUI (SSD patients ITT Population)
- Table 14.2.10.5 APHAB (SSD patients ITT Population)
- Table 14.2.10.6 The Speech, Spatial and Qualities of Hearing Scale (SSQ) (SSD patients ITT Population)
- Table 14.2.11.1 Threshold Audiometry - Free field ATB System vs Unaided (Conductive/Mixed patients ITT Population)
- Table 14.2.11.2 Adaptive speech recognition in noise and Speech in quiet ATB System vs Unaided (Conductive/Mixed patients ITT Population)
- Table 14.2.11.3 BC Direct (Conductive/Mixed patients ITT Population)
- Table 14.2.11.4 HUI (Conductive/Mixed patients ITT Population)
- Table 14.2.11.5 APHAB (Conductive/Mixed patients ITT Population)
- Table 14.2.11.6 The Speech, Spatial and Qualities of Hearing Scale (SSQ) (Conductive/Mixed patients ITT Population)
- Table 14.2.12.1 Threshold Audiometry - Free field ATB System vs Softband (ITT Population)
- Table 14.2.12.2 Threshold Audiometry - Free field ATB System vs Softband (PP Population)
- Table 14.2.12.3 Threshold Audiometry - Free field ATB System vs Softband (Conductive/Mixed patients ITT Population)
- Table 14.2.12.4 Threshold Audiometry - Free field ATB System vs Softband (SSD patients ITT Population)
- Table 14.2.13.1 Adaptive speech recognition in noise and Speech in quiet ATB System vs Softband (ITT Population)
- Table 14.2.13.2 Adaptive speech recognition in noise and Speech in quiet ATB System vs Softband (PP Population)
- Table 14.2.13.3 Adaptive speech recognition in noise and Speech in quiet ATB System vs Softband (SSD patients ITT Population)
- Table 14.2.13.4 Adaptive speech recognition in noise and Speech in quiet ATB System vs Softband (Conductive/Mixed patients ITT Population)
- Table 14.3.1.1 Summary of Adverse Events (Safety Population)
- Table 14.3.1.2 Adverse Events (AE), by CTCAE Term (Safety Population)
- Table 14.3.1.3 Adverse Device Events (ADE), by CTCAE Term (Safety Population)
- Table 14.3.1.4 Serious Adverse Events (SAE), by CTCAE Term (Safety Population)
- Table 14.3.1.5 Serious Adverse Device Events (SADE), by CTCAE Term (Safety Population)
- Table 14.3.2 Pain and Numbness (Safety Population)
- Table 14.3.3 Device deficiency (Safety Population)

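### SAP section 6 declares no changes from the protocol, yet the SAP tests the device against the Softband, which protocol 10.5.2 rules out, and departs from CIP version 5 on several other points

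*SAP*

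**What the plan says.** Protocol 10.5.2 limits the secondary efficacy analyses to device against unaided and adds a rule for the reference device: "Baha BP110 Power Sound Processor on a Baha Softband will be presented (where applicable) but not compared to Investigational Device".

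The SAP plans the opposite. Section 4.1 ranks "Investigational Device vs. Baha power sound processor on a Baha Softband" as the second analysis priority. Section 4.10.2 states that "Comparison of the Investigational device with a Baha Power sound processor worn on a Baha Softband will be done according to the general methodology", by paired permutation test, for PTA4, single-frequency thresholds, speech in noise, speech in quiet and BC Direct. Section 7.1 lists eight tables titled against the Softband, the first being "Threshold Audiometry - Free field ATB System vs Softband (ITT Population". Section 4.1 also sets the level and direction of every test: "All significance tests will be one-sided and performed at the 2.5% significance level to demonstrate an improvement with Investigational Device".

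SAP section 6 then reads, in full: "No changes of the analyses according to the protocol are made".

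**The concern.** Section 6 is where a reader looks for departures from the protocol. Told there are none, that reader would take the Softband p-values as protocol-planned, and could over-read a nominally significant one. Once section 6 fails on one point, the rest of the SAP has to be checked against the protocol. That check turns up five more differences. They vary in weight: one governs when a primary endpoint may be called confirmative, one produces tests with no observed data behind them, one leaves collected safety data unsummarised at the main safety time point, and two are small.

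**Working it through.** The plan gives no figure on this point to reproduce. The check is to set the texts side by side and then count the Softband tests.

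| | Protocol (CIP version 5) | SAP 1.0 |
|---|---|---|
| (a) Softband | 10.5.2: shown, not compared; 10.1.2: the objective is to measure | 4.1: second priority; 4.10.2: tested; 7.1: tables 14.2.12.1-4 and 14.2.13.1-4 |
| (b) APHAB, HUI, SSQ | 6.5 to 6.7 and section 8: Visits 1, 6 and 8 (pre-op, 3 and 12 months) | 3.2.2 and 4.10.2: 3, 6 and 12 months |
| (c) Bone-conduction audiogram after surgery | 5.5, 6.1 and section 8: Visits 6, 7 and 8 (3, 6 and 12 months) | 3.3.4, 4.11.4 and 7.1: Visits 6 and 8 only |
| (d) Adverse event summaries | 10.6.2: predefined event, System Organ Class, Preferred Term | 4.11.2 and 7.1: CTCAE term |
| (e) General one-sided level | 10.4: 5%; but 10.3.1, 10.3.2 and 10.5.1: 0.025 | 4.1: 2.5% |
| (f) Primary success in an arm | 10.5.1: both must be significant | 4.10.1: the same; 4.1: stepwise, PTA4 first |

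**Count for (a).** Inputs are the variables and visits in SAP 4.10.2 and the BC Direct frequencies in SAP 1.1.

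- PTA4: 1 x 4 visits = 4
- Single frequencies: 7 x 4 = 28
- Speech in noise: 1 x 4 = 4
- Speech in quiet: 3 levels x 4 = 12
- Subtotal: 4 + 28 + 4 + 12 = 48 per analysis set
- BC Direct: 9 frequencies x 5 visits = 45, giving 48 + 45 = 93

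The range is needed because 4.10.2 lists BC Direct in the Softband comparison but names no frequencies there, and no BC Direct table carries the Softband in its title. There are four analysis sets: pooled ITT, pooled PP, and each arm within ITT. Protocol 10.5.2 provides for none of these tests.

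If there were no difference, the expected number of nominally significant results per set is tests x 0.025: 48 x 0.025 = 1.2, and 93 x 0.025 = 2.325, about 2.3. Expectations add whatever the correlation, so no independence is assumed.

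**(b)** No 6-month questionnaire value is scheduled. Under the imputation rules in SAP 4.1, read literally, a value missing between two visits is interpolated and one missing at the end is carried forward. Every 6-month value would therefore be imputed from the 3-month value, with or without the 12-month one. A p-value at 6 months would carry no information of its own.

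**(c)** Visit 7 is the 6-month visit, and SAP 4.11 places the primary safety analysis there. The thresholds are collected but neither listed nor tabulated for it.

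**(f)** Take an arm where PTA4 is significant at 0.025 and speech in noise is not. Under SAP 4.1 the steps before the first failure stay confirmative, so PTA4 is confirmative. Under protocol 10.5.1 and SAP 4.10.1 the primary analysis in that arm is not. Both of those sections write SIQ for the second endpoint, an abbreviation that neither document defines; I read it as speech in noise, which the same paragraph names. If it meant speech in quiet the conflict would remain, since PTA4 alone would still not suffice. Either rule holds the one-sided error within an arm at 0.025, so what differs is the claim allowed, not the error rate.

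**The case against.** **The protocol is itself mixed.** Its aim (1.2) speaks of "audiological test results with a Baha BP110 Power Sound Processor on a Baha Softband in relation to the Investigational device"; its design section (4.1) says "Each subject will be compared to his/her own preoperative unaided hearing situation, with the Baha BP110 Power Sound Processor on a softband preoperatively"; and 4.2 notes that a comparative design may be needed. One can argue that the SAP merely settled an internal conflict. Part of this stands: the protocol wording also needs tidying. But the aim is to measure and present, 4.2 fixes no test or margin, 2.1.2 says there is no comparator, and 10.2 and 10.3 hold no Softband hypothesis or sample size. Section 10.5.2 is the only explicit rule for analysing the Softband data. Section 10.10 leaves detail to the SAP, not an analysis that 10.5.2 excludes. Settling the conflict would still be a change to declare.

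**The tests are not confirmative.** This stands. A reader might infer from the general sentence on direction that the SAP sets out to claim superiority over the Softband, or that these tests inflate the confirmative error rate. The documents support neither: every formal hypothesis in SAP 4.10.1 and 4.10.2 is against the unaided or preoperative situation, and SAP 4.1 confines confirmative statements to six steps, none involving the Softband. Nor is a familywise error figure warranted: the tests reuse the same subjects across visits and frequencies, so one computed as if they were independent would mislead.

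**The 6-month safety signal is not lost.** This also stands. Protocol 7.2.4 makes a shift above 15 dB at any frequency an adverse event, so such shifts reach the 6-month event summaries. What is missing is the summary of the thresholds.

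**Nothing is concealed.** True: the Softband tests, the 6-month analyses and the 2.5% level are all printed in the SAP. The fault is that section 6 denies any difference.

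**The SAP names no CIP version.** It also describes fitting software 1.0.3, while CIP version 5 has 1.02. The finding is therefore stated against version 5, the version supplied.

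**Conclusion.** Against CIP version 5, SAP section 6 is incorrect. The Softband tests (a) contradict protocol 10.5.2: 48 to 93 per analysis set, with about 1.2 to 2.3 expected to reach 0.025 if there were no difference. They do not touch the primary claims.

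Of the rest, (f) matters most, because it decides whether PTA4 can be called confirmative alone; it should not be passed off as added detail. Item (b) plans tests on wholly imputed values. Item (c) is a reporting gap at the primary safety time point. Item (d) is minor. Item (e) is mainly an inconsistency within the protocol, on which the SAP takes the stricter value.

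The count assumes that each listed variable is tested once per listed visit; its upper end assumes BC Direct at nine frequencies. Item (b) assumes that the imputation rules apply to a visit with no scheduled assessment, which the SAP does not exclude.

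**What to change.** In the SAP:

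1. Present the Softband results by condition, without tests, as protocol 10.5.2 says. If the comparison is wanted, declare it in section 6 as exploratory and unadjusted for multiplicity, and amend 10.5.2.
2. Delete the 6-month APHAB, HUI and SSQ analyses from 3.2.2 and 4.10.2.
3. Add Visit 7 to the bone-conduction audiogram in 3.3.4, 4.11.4 and the tables.
4. State in 4.1 that neither primary endpoint is confirmative in an arm unless both are significant, and in 4.10.1 replace SIQ by the endpoint meant.
5. Summarise adverse events as in protocol 10.6.2, or give the reason for CTCAE terms.
6. Replace section 6 with a list of all differences from CIP version 5, naming that version.

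In the protocol, correct 5% to 2.5% in 10.4, and SIQ in 10.5.1, at the next amendment.

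The cost is wording and a few table shells; no new data. The sponsor gives up or downgrades the Softband p-values. The SAP-only route for item 1 avoids an amendment, which under protocol 11.3 and 12.6.1 needs ethics and authority approval before it takes effect.

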2.3.5 Reference device

The ATB System will provide similar output and audiological performance as the Cochlear Baha BP110 Power Sound Processor. The BP110 Power Sound Process will be used as reference device in this clinical investigation. The BP110 Sound Processor on a Softband will be used at the first visit for the subject, before the surgery visit, to measure preoperative Sound Processor performance and to prepare the subject for the postoperative hearing situation. The BP110 Sound Processor is a fully programmable, head-worn sound processor, with automatic signal processing, which is regulatory approved for use together with Baha systems (Baha Connect and Baha Attract) and together with a Baha Softband (Figure 9). This sound processor is secured to the Baha Softband by means of a snap coupling. The sound processor has several automatic systems, including active feedback cancellation through phase cancellation, automatic adaptive multi-band directional microphones, wide dynamic range compression and automatic noise management. The transducer is driven by a size 675 battery.

Figure 9. Cochlear Baha BP110 Power Sound Processor and Baha Softband

All other non-investigational devices, are listed in Appendix 2.

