4.2 Justification for the design of the clinical investigation

The design where the primary assessment consist of a comparison of the post-operative aided performance with the preoperative unaided performance is considered relevant for this purpose. The primary efficacy assessment of the investigation, i.e. threshold, free-field, pure tone average PTA4, is a relevant and objective method used by clinics internationally as a way to assess hearing performance. The test is not language specific (no words used), thus rendering comparative data in an international, multilingual setting.

The self-reported assessment of hearing outcome using the APHAB questionnaire was chosen as an important secondary efficacy assessment; hence, the APHAB scale was used for determination of the sample size in the investigation⁹. The APHAB has been used in investigations previously and has shown to be a good tool for measuring changes in patient benefits.

The rationale for measuring and collect data with Baha BP110 Power Sound Processor on a Softband as a secondary assessment is based on the fact that the FDA guideline for middle ear implants suggests that a comparative non-inferiority or superiority study design (using within-patient comparison) may be required.

The Baha BP110 Power Sound processor on a Softband was chosen for a secondary assessment, since the ATB System mimics the performance of a Baha Power Sound Processor (with the same 55 dB fitting range) on the passive transcutaneous Baha Attract System¹. Therefore it is also a relevant choice to present as a postoperative hearing situation for the subject.

This investigation is limited to adult subjects. The paediatric population constitutes an inhomogeneous patient group (age-related), and currently there are no audiological tests that are suitable for comparisons across age ranges and across multiple countries/languages.

The follow-up period of 12 weeks post-surgery, 8 weeks post fitting for the primary analysis is chosen as it is judged as long enough for the subjects to adapt and get used to the hearing performance with this investigational device. The total length of the investigation is judged long enough to collect hearing performance and safety data as long term data.

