5.9 Sound Processor fitting

The Baha Fitting Software 4.0 SR2⁸ will be used at visit 1 when the fitting procedure should be performed for the Baha BP110 Power Sound Processor as a reference device.

The Osia Fitting Software 1.02⁷ will be used to adjust the investigational device sound processor settings for a specific subject. This will happen during Visit 4 when tests will be performed, and throughout the study. The fitting software will be installed on a lap-top provided by the Sponsor, and the fitting-data will be saved on the lap-top until study is ended when it will be transferred to the Sponsor in a coded way.

The Digital Link Calibration (e.g. coil-to-coil measurement) that is a step in the connection step in the Osia Fitting Software, should be performed at each occasion that the software is being used to fit or fine tune the device to optimize the performance of the device throughout the study. This will also provide an indication of the soft tissue thickness.

For the sound processors Individual Stable Gain (e.g. feedback measurements as part of the Fitting Software) the Feedback Analyser should be performed at each occasion that the software is being used to fit or fine tune the device to optimize the performance of the device throughout the study. For the Investigational device this data will be collected, saved and eventually transferred to the Sponsor for analysis.

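### SAP 4.10.2 tests the device after months of wear against a Softband processor measured once at first fitting, so adaptation can contribute to an apparent device advantage at 3, 6 and 12 months

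*SAP*

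**What the plan says.** **Softband.** Protocol 2.3.5: "The BP110 Sound Processor on a Softband will be used at the first visit for the subject, before the surgery visit". Protocol 5.9 places its fitting at the same visit: the Baha software "will be used at visit 1 when the fitting procedure should be performed for the Baha BP110 Power Sound Processor as a reference device". Protocol 6.2 to 6.4 schedule Softband thresholds, speech in quiet and speech in noise at Visit 1 only. No wear period comes before these tests.

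**Device.** It is fitted and first tested at Visit 4, four weeks after surgery, and retested at 3, 6 and 12 months (Protocol 5.9 and 6.2 to 6.4). Protocol 4.2 explains the primary time point by wear: "8 weeks post fitting for the primary analysis is chosen as it is judged as long enough for the subjects to adapt".

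**Comparison.** SAP 4.10.2 specifies a paired permutation test: "Comparison of the Investigational device with a Baha Power sound processor worn on a Baha Softband will be done according to the general methodology". It covers PTA4, seven single frequencies, speech in quiet at three levels and speech in noise, the last listed as "Adaptive speech recognition in noise (50% performance) at 4 weeks, 3, 6 and 12 months". It also covers "BC Direct at 4 and 6 weeks, 3, 6 and 12 months". SAP 4.1 makes every test one-sided at 2.5% in the direction of benefit from the device, and ranks the Softband comparison second after unaided. The six-step hierarchy in SAP 4.1 contains no Softband step.

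**Protocol position.** Protocol 10.5.2 has the Softband results shown where applicable and states that they are not compared with the device. SAP section 6 declares no departures from the protocol.

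**The concern.** The two sides of the contrast differ in more than the device. At 3, 6 and 12 months the subject has lived with the device, whereas the Softband was measured minutes or hours after fitting. Protocol 4.2 itself treats wear time as relevant to performance with the device. If performance rises with wear, the rise enters the difference in the direction that the one-sided test rewards. Pairing does not remove this, because the imbalance lies within each subject. The SAP neither prefers a visit nor attaches a caveat.

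At stake is how the Softband results will be read. Presenting them in relation to the device is a stated aim (Protocol 1.2). Protocol 4.2 links their collection to a guideline under which a within-patient non-inferiority or superiority design might be asked for. SAP 7.1 reserves eight tables for the contrast (14.2.12.1 to 14.2.12.4 and 14.2.13.1 to 14.2.13.4).

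**Working it through.** **1. Wear time at each comparison**

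Inputs: device fitting at week 4 (±1 week); visit windows ±2 weeks at 3 months, ±3 at 6 months and ±4 at 12 months (Protocol section 8). Wear = visit time − fitting time.

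- 3 months: 12 − 4 = 8 weeks, which reproduces the figure in Protocol 4.2. Shortest: (12 − 2) − (4 + 1) = 5. Longest: (12 + 2) − (4 − 1) = 11. If 3 months is read as 13 weeks: 9, range 6 to 12.
- 6 months: 26 − 4 = 22 weeks, range 18 to 26.
- 12 months: 52 − 4 = 48 weeks, range 43 to 53.
- Week 6 (BC Direct only): 6 − 4 = 2 weeks.
- Week 4: 0 weeks.
- Softband at Visit 1: 0 weeks.

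Wear is therefore equal only at week 4.

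**2. How often the test rejects if the devices are equal and only adaptation differs**

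Inputs from the documents:
- One-sided level 0.025 (SAP 4.1). Protocol 10.4 gives 5% for all tests; the SAP level is used here.
- n = 50 in total and at least 13 per arm (SAP 1.5.3).
- SD 11.3 for the unaided-to-device change in SNR (SAP 1.5.1).

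Assumptions, because the documents give no figure:
- Adaptation gain d of 1 to 2 dB.
- The SD of the device-Softband difference. The value 11.3 is borrowed; 5 and 3 are shown for range.

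Formula, with the paired t-test standing in for the permutation test on normal data: P(reject) = 1 − F(t(0.975, n−1); n−1, λ), where F is the noncentral t distribution function and λ = d√n / SD.

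For SD 11.3:
- n = 13: λ = 1 × 3.606 / 11.3 = 0.319 for d = 1, and 0.638 for d = 2.
- n = 50: λ = 1 × 7.071 / 11.3 = 0.626 for d = 1, and 1.252 for d = 2.

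| n | SD | d = 1 dB | d = 2 dB |
|---|---|---|---|
| 13 | 11.3 | 4.8% | 8.5% |
| 50 | 11.3 | 8.9% | 23.2% |
| 13 | 5 | 9.8% | 26.4% |
| 50 | 5 | 28.3% | 79.2% |
| 13 | 3 | 19.7% | 59.8% |
| 50 | 3 | 63.7% | 99.6% |

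At d = 0 the rate is 2.5% throughout. At d = 0.5 and SD 11.3 it is 3.5% (n = 13) and 4.9% (n = 50), so a small gain with a large SD does little harm. These figures are for the SNR scale and do not carry over to the thresholds.

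**3. The two documents side by side**

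Protocol 10.5.2: Softband results shown, no comparison with the device. SAP 4.1 and 4.10.2: comparison tested at up to five time points. SAP section 6: no changes. These statements cannot all stand.

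**The case against.** **The protocol already excludes the comparison.** If the SAP is brought into line, the p-values disappear and a labelling question remains. This stands, and it is why reconciliation comes first in the fix. It does not remove the point: values shown side by side still carry unequal wear. The protocol is also not wholly clear, since its section 4.1 describes each subject being compared "with the Baha BP110 Power Sound Processor on a softband preoperatively and with the Investigational device at 3 months".

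**Adaptation may be small.** Every subject must have prior experience of fitted amplification, which may include a bone conduction device on a softband (Protocol 3.1.1). The adaptation statement in Protocol 4.2 concerns the investigational device only. Nothing in the documents shows that wear shifts detection thresholds or BC Direct. All of this stands. It limits the size of the effect and points to the speech tests as the likeliest place for it.

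**Week 4 is not a clean alternative.** A reader might infer that week 4 is the one like-for-like comparison. The documents do not support that. It matches on wear time only. It falls four weeks after surgery, while Protocol 6.1 places postoperative bone conduction testing at 3 and 6 months, when healing and swelling are expected to have settled. It always follows the Visit 1 runs, so order and practice still differ. Fitting and magnet choice continue at later visits. Week 4 may be biased against the device.

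**The preoperative-only Softband measure is an open design feature.** This stands too. Showing it beside the adapted device is defensible if the difference in wear is stated.

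**Conclusion.** The imbalance is documented: 0 weeks of scheduled Softband wear against nominally 8, about 22 and about 48 weeks for the device, tested one-sided for improvement with no caveat. Device effect and adaptation cannot be separated at those visits, and any adaptation gain acts in the device's favour. Under an assumed gain of 1 to 2 dB and a borrowed SD of 11.3, false rejection is about 5-9% at n = 13 and 9-23% at n = 50, instead of 2.5%; a smaller SD raises it. Both the gain and the SD are assumptions.

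A reader might infer that the plan will turn adaptation into a superiority claim. The documents do not support that. The Softband tests lie outside the hierarchy, so no result is confirmative; no superiority or non-inferiority hypothesis or margin against the Softband is stated; and the size of adaptation is unknown. What the documents support is that adaptation can contribute to an apparent advantage in exploratory tests which the protocol says are not to be made. The change of device fitting software during the study (SAP 4.12) is a further difference at the later visits.

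**What to change.** 1. Reconcile SAP 4.1 (priority 2) and 4.10.2 with Protocol 10.5.2.
2. Present device against Softband at 3, 6 and 12 months, and BC Direct after week 4, descriptively without p-values.
3. Add a footnote to the Softband tables giving device wear time at each visit and stating that the Softband was measured at first fitting.
4. Show week 4 beside these results as the equal-wear contrast, labelled exploratory, with its limits stated: four weeks after surgery, healing, fixed test order.
5. If any Softband test is kept, declare it in SAP section 6 as a change from the protocol, and do not read it as device superiority.

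Cost: SAP wording and table footnotes; no new data, since week 4 is already collected and listed. Apart from BC Direct, the tests given up number 1 + 7 + 1 + 3 = 12 per visit, or 36 over the three later visits in each analysis set. Downside: there will be no p-values against the Softband at later visits. The week-4 contrast may look less favourable to the device, and may be biased against it by incomplete healing.
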